**Footnotes:**

CBC=complete blood count; CT=computed tomography; D=days; ECOG=Eastern Cooperative Oncology Group; ICS = informed consent; MFSI-SF= Multidimensional Fatigue Symptom Inventory-Short Form

1. Serum chemistries (creatinine, glucose, total protein, blood urea nitrogen [BUN], total carbon dioxide [CO2], albumin, total bilirubin, alkaline phosphatase, and aspartate transaminase [AST] and alanine transaminase [ALT]) and electrolytes (total calcium, chloride, potassium, sodium)
2. All subjects will have PT/INR/aPTT at screening and End of Treatment Visit. ONLY subjects who are prophylactically treated with an agent such as warfarin or heparin must have close monitoring on Cycle 1 Day 5 and Day 1 of each cycle. If either of these values is above the therapeutic range, subjects should have at least weekly evaluations until INR/PTT is stable based on a measurement that is pre-dose as defined by the local standard of care.
3. Complete only for women of childbearing potential
4. Baseline CTs must be completed within 28 days prior to registration. CTs for re-staging will be performed after Cycle 2 (8 weeks) is complete and may be performed  $\pm$  5 days of scheduled clinic visit. Regardless of randomization, all subjects will follow up with their physician to discuss results.
5. Regorafenib 160 mg PO once daily will be administered for 3 weeks on/1 week off. If subject randomizes to receive Ginseng: 2,000 mg PO per day (1,000 mg BID), every day of each 28-day cycle. For subjects that randomize to ginseng, if regorafenib is held due to toxicity the ginseng may continue per protocol schedule.
6. See Study Procedures Manual for MFSI-SF and PROMIS questionnaires and additional information. The research nurse will provide the questionnaires to the subject as well as instructions on completion of the questionnaires. These instructions should include the importance of the subject completing the surveys without family assistance. The first set of surveys will be administered by the research nurse in the clinic via interview. The remainder of the surveys will be self-administered by the subject in clinic. If the subject has a question regarding the surveys the research nurse or physician will be available to respond. For pill count, please ask the subject to bring their pill bottle to verify number of doses taken at the time of clinic visit.
7. The End of Treatment visit should occur 30 days after completion of Cycle 2 ( $\pm$  7 days). Subjects who stop treatment prior to completion of Cycle 2 should have the EOT 30 days after discontinuation of treatment. Subjects who have an ongoing  $\geq$  grade 2 or serious AE (SAE) at this visit will continue to be followed until the AE resolves to  $\leq$  Grade 1 or baseline, deemed clinically insignificant, and/or until a new anti-cancer treatment starts, whichever is earlier.
8. Follow up will occur in all subjects after completion of Cycle 2 every 3 months for 18 months. Follow up may be accomplished via clinic visit, phone call, or other avenues as appropriate.
9. Day -7 only ECOG performance status need be obtained.
10. Urinalysis should be done if proteinuria is suspected as per site investigator's discretion.

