## 3. ELIGIBILITY CRITERIA

### 3.1. Inclusion Criteria

1. Subjects must be able to understand and be willing to sign the written informed consent and HIPAA authorization for release of personal health information. A signed informed consent form must be appropriately obtained prior to the conduct of any trial-specific procedure.  
**NOTE:** HIPAA authorization may be included in the informed consent or obtained separately.
2. Age  $\geq$  18 years at the time of consent.
3. Life expectancy of at least 12 weeks (3 months) as determined by the treating physician.
4. ECOG Performance Status of 0 or 1 within 28 days prior to registration.
5. Histological or pathologically confirmed stage IV adenocarcinoma of the colon.

6. Adequate bone marrow, liver and renal function as assessed by the following laboratory values obtained within 7 days prior to registration for protocol therapy.
  - Absolute neutrophil count (ANC) count  $> 1,500/\text{mm}^3$
  - Hemoglobin (Hgb)  $> 9\text{g/dL}$
  - Platelet count  $> 100,000/\text{mm}^3$
  - Total bilirubin  $\leq 1.5 \times$  the upper limit of normal (ULN).
  - Alanine aminotransferase (ALT) and aspartate amino-transferase (AST)  $\leq 2.5 \times$  ULN ( $\leq 5 \times$  ULN for subjects with liver involvement of their cancer)
  - Alkaline phosphatase limit  $\leq 2.5 \times$  ULN ( $\leq 5 \times$  ULN for subjects with liver involvement of their cancer)
  - Serum creatinine  $\leq 1.5 \times$  the ULN
  - International normalized ratio (INR)/Partial thromboplastin time (PTT)  $< 1.5 \times$  ULN.  
**NOTE:** Subjects who are prophylactically treated with an agent such as warfarin or heparin will be allowed to participate if no prior evidence of underlying abnormality in coagulation parameters exists. Close monitoring of at least weekly evaluations will be performed until INR/PTT is stable based on a measurement that is pre-dose as defined by the local standard of care. Warfarin dose should not exceed 1 mg
7. Women of childbearing potential must have a negative serum pregnancy test performed within 7 days prior to the start of study drug. Post-menopausal women (defined as no menses for at least 1 year) and surgically sterilized women are not required to undergo a pregnancy test.

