### **7.2.3 Cycle 2 Day 1 ( $\pm 3$ days)**

- Complete physical examination
- Vital signs including BP, weight and ECOG performance status
- Laboratory testing:
  - Complete Blood Count (CBC) with differential and platelet count
  - Complete metabolic profile (CMP)
  - PT/INR and aPTT
  - Urinalysis should be done if proteinuria is suspected as per site investigator's discretion.
- Adverse event and concomitant medication assessment
- Drug administration as outlined in Section 5 and Study Calendar
- Administer MFSI-SF and PROMIS questionnaires
- Pill Count

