## **Precautions**

Ginseng is known to interfere with blood coagulation and some components of ginseng can elevate plasma insulin levels, causing hypoglycemia. Treating physicians should closely monitor persons with hypoglycemia or those on anticoagulants per local standard of care.

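### For subjects on prophylactic anticoagulants, inclusion criterion 6 starts weekly INR/PTT checks without a trigger, but calendar footnote 2 starts them only after an above-range value

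*Combined protocol and SAP*

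**What the plan says.** Four places in the protocol set coagulation testing.

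- **Inclusion criterion 6, INR/PTT note (synopsis and section 3.1).** Subjects on prophylactic warfarin or heparin may take part if they have no earlier sign of a coagulation abnormality. The note then adds: "Close monitoring of at least weekly evaluations will be performed until INR/PTT is stable based on a measurement that is pre-dose", with local standard of care settling what that means.
- **Section 7 calendar, footnote 2.** For everyone: "All subjects will have PT/INR/aPTT at screening and End of Treatment Visit". Only the prophylactically treated subjects "must have close monitoring on Cycle 1 Day 5 and Day 1 of each cycle". The footnote continues: "If either of these values is above the therapeutic range, subjects should have at least weekly evaluations until INR/PTT is stable".
- **Section 7 calendar table.** The coagulation row has an entry at the day -7 screening column, a bracketed D5 under Cycle 1, a bracketed X at Cycle 2 Day 1, and an X at End of Treatment. It has nothing at either Day 15 visit.
- **Visit lists, sections 7.2.1 to 7.2.4.** Only section 7.2.3 (Cycle 2 Day 1) lists "PT/INR and aPTT", and it does not restrict the test to any subgroup. No list has a Day 5 entry, and section 7.2.1 lists no coagulation test on Cycle 1 Day 1.

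Section 3.3 adds that warfarin users are to be monitored regularly, without an interval.

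**The concern.** The inclusion note and the footnote address the same subjects but differ in what starts weekly testing. In the note, weekly testing applies from the outset and ends at stability. In the footnote, it begins only once a value is above range. A site working from the eligibility section and a site working from the calendar could therefore test the same kind of subject at different frequencies, and each could point to the protocol. A site working from the visit lists alone would not find the Day 5 test at all.

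The protocol itself treats these subjects as at risk. Section 3.3 reports bleeding or raised PT-INR in some subjects taking warfarin with regorafenib, section 5.1.4 says regorafenib may affect warfarin levels, and section 9.1 (Precautions) states: "Ginseng is known to interfere with blood coagulation". At stake are the safety of this subgroup and uniform detection of coagulation abnormalities across sites. The second point has some bearing on the secondary objective of comparing toxicities between arms.

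**Working it through.** The documents state no interval between tests, so there is no figure of the plan's to reproduce. What follows is study-day arithmetic plus a comparison of the texts.

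**Inputs.** Cycle length is 28 days (section 7). The footnote's fixed on-treatment tests are Cycle 1 Day 5 and Day 1 of each cycle. The window at Cycle 2 Day 1 is ±3 days (section 7.2.3).

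**Interval between the fixed tests**
- Cycle 2 Day 1 = 28 + 1 = study day 29.
- Day 5 to Cycle 2 Day 1 = 29 − 5 = 24 days.
- With the window: (29 − 3) − 5 = 21 days to (29 + 3) − 5 = 27 days.

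**Weekly rule over the same interval**
- Steps of 7 from day 5 give days 12, 19 and 26: three evaluations before day 29. The calendar has no coagulation entry for any of them.

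**Who is affected on Day 5**

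| Status on Day 5 | Inclusion note | Footnote 2 | Conflict? |
|---|---|---|---|
| Above range | Weekly until stable | Weekly until stable | No |
| Not above range, stable | No further weekly tests required | Next test Cycle 2 Day 1 | No |
| Not above range, not yet shown stable | Weekly until stable | Next test Cycle 2 Day 1 | Yes |

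The period before the Day 5 result is also affected, because the note's weekly rule is already running and the footnote's is not.

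**Calendar against visit lists**
- *Day 5:* in the table and footnote 2; in none of sections 7.2.1 to 7.2.4.
- *Cycle 1 Day 1:* implied by the footnote's Day 1 of each cycle. The table shows only the bracketed D5 in Cycle 1, and section 7.2.1 lists no coagulation test.
- *Cycle 2 Day 1:* bracketed in the table and limited to anticoagulated subjects by the footnote, but unrestricted in section 7.2.3. The timing agrees; the population does not.

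**The case against.** The strongest reply is that the two main texts are close. Both contain an at-least-weekly rule that ends at stability as judged locally, and entry already narrows the group: INR/PTT below 1.5 × ULN, no earlier coagulation abnormality, no therapeutic anticoagulation, and warfarin limited to 1 mg. Other safeguards exist: regular monitoring of warfarin users (section 3.3), proactive monitoring of narrow-index drugs (section 5.1.4), close monitoring of those on anticoagulants (section 9.1), and adverse event review at both Day 15 visits. The missing Cycle 1 Day 1 test may also be partly covered, since section 7.2.1 lets recent testing stand if done within 7 days of starting therapy.

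Most of this stands and limits the point. It does not remove the difference in trigger, and the general safeguards give no interval that would settle which rule a site follows.

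A reader might infer more than the documents support:
- *That every anticoagulated subject faces a 24-day gap.* Footnote 2 keeps weekly checks for those above range, and a subject stable by Day 5 needs no weekly test under either text.
- *That weekly testing is a condition of enrolment.* The entry condition is the absence of an earlier coagulation abnormality; the weekly sentence describes monitoring on study.
- *That section 7.2.3 gives a third schedule.* It names the same visit as the footnote. At worst, other subjects have an extra test.
- *That subjects go 50 to 57 days on drug untested after Cycle 2 Day 1.* With no delays, regorafenib ends on day 28 + 21 = 49 and ginseng on day 56. A visit 30 days later falls on day 79 or 86, so the intervals are 79 − 29 = 50 and 86 − 29 = 57 days, but 30 days of each follow the dose used as the reference.
- *That a change early in Cycle 1 is bound to go unseen.* The footnote sets a Day 5 test for exactly these subjects; the weakness is that the visit lists omit it.

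**Conclusion.** The inconsistency is real and narrow. The inclusion note and footnote 2 give different rules for subjects on prophylactic anticoagulants who are not above range but not yet shown to be stable. For them the choice of text decides between no scheduled test for 24 days (21 to 27 with the window) and tests at about days 12, 19 and 26. The calendar and the visit lists also disagree on the Day 5 test, the Cycle 1 Day 1 test, and who is tested at Cycle 2 Day 1.

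The arithmetic assumes cycles run without delay and, for the three weekly dates, that the subject remains unstable until Cycle 2 Day 1. The documents give neither the number of anticoagulated subjects nor a common definition of stable, so the number affected cannot be estimated.

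The fatigue endpoint, the sample size and the primary analysis are unaffected. Section 11 compares toxicities by Fisher exact tests and plans no analysis of coagulation values, so any effect on results is limited to how evenly abnormalities are detected. The point should be corrected because sites following different passages would test differently in a group that the protocol flags as at risk.

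**What to change.** Reconcile the criterion 6 note (synopsis and section 3.1), the section 7 table, footnote 2, and sections 7.2.1 to 7.2.4 so that they state:

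1. one coagulation schedule for subjects on prophylactic anticoagulants, with every required test, including any on Cycle 1 Day 1 or Day 5, shown in both the table and the visit lists;
2. one rule for what starts weekly evaluations and what ends them. If the therapeutic range stays as the trigger, the protocol should define it;
3. one target population for the Cycle 2 Day 1 test.

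Which schedule and trigger are right is a clinical decision for the sponsor, and this review takes no position on it.

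The cost is amendment wording and a matching update of the visit forms. Depending on the sponsor's choice, there may be a few extra routine blood tests in this subset: up to three between Day 5 and Cycle 2 Day 1 for a subject who is not above range and stays unstable throughout that interval.

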## 7.2 On Treatment

### 7.2.1 Cycle 1 Day 1

**NOTE:** Cycle 1 Day 1 testing need not be repeated if completed within 7 days of starting protocol therapy.

- Complete physical examination
- Vital signs including BP, weight and ECOG performance status
- Adverse event and concomitant medication assessment
- MFSI-SF and PROMIS questionnaires
- Drug administration as outlined in Section 5 and Study Calendar

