## **11 STATISTICAL CONSIDERATIONS**

### **Power/Sample Size:**

The pilot study will enroll 90 total subjects and randomize them using a 2:1 allocation with 60 subjects enrolled in the Regorafenib + Ginseng group and 30 enrolled in the regorafenib + no ginseng group. The sample size is calculated based on the MFSI-SF fatigue endpoint. Based on the data published in Barton et al (2013), the expected standard deviations for the outcome of interest are 27.0 for the Ginseng group and 26.1 for the no ginseng group. Using a two group Satterthwaite t-test with a 0.050 two-sided significance level, there is 80% power to detect a difference between groups if the change in the no ginseng group is 10 and the change in the Ginseng group is 27 (or greater) (a group difference of 17 units). In addition, with this sample size, a two-sided 95.0% confidence interval for the difference of the two means (change in fatigue score for Ginseng group vs. change in fatigue score for no ginseng group) will extend 11.833 from the observed difference in means, assuming that the common standard deviation is 27.0 (conservatively choosing the standard deviation from the Ginseng group since it is larger than the no ginseng standard deviation) when the sample sizes are 60 and 30 respectively (a total sample size of 90) and the confidence interval is based on the large sample z statistic.

Based on previous published data [1] we believe that the Ginseng mean change in fatigue score will likely be closer to 20 (rather than 27); thus, we do not anticipate that this trial will reach

statistical significance. However, we will be able to refine our estimate of the standard deviation for the fatigue score in this subject population and provide a 95% confidence interval to estimate the likely boundaries for the true effect size. This information, along with estimates of retention and adherence, can be used to determine the sample size for further evaluation.

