### **Analyses:**

The primary objective is to assess the effect of Ginseng on fatigue using the multidimensional Fatigue Symptom Inventory–Short Form (MFSI-SF) and PROMIS Short Form v1.0 – Fatigue 8a. Subjects will have fatigue assessed at baseline and at weeks 2, 4, and 8. Repeated measures analysis of covariance will be used to assess the effect of Ginseng on fatigue. An unstructured covariance matrix will be used initially to account for the within subject correlation in fatigue over time. Additional covariance structures (exchangeable, autoregressive, Toeplitz, etc.) will be considered to reduce the number of fitted parameters, and the final structure will be chosen based on likelihood ratio tests for nested structures and the AIC statistic for non-nested structures. The primary hypothesis will be assessed using a linear contrast at the end of cycle 1. Additional contrasts will be used to assess the difference in fatigue at each time as well as the average difference in fatigue over time.

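### Baseline fatigue is taken by nurse interview and every later score by self-completion, so mode is confounded with time: within-arm change and precision suffer modestly, while the between-arm contrast is protected from a shift common to both arms

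*Combined protocol and SAP*

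**What the plan says.** Footnote 6 to the schedule in Section 7 sets two modes in consecutive sentences: "The first set of surveys will be administered by the research nurse in the clinic via interview", and then "The remainder of the surveys will be self-administered by the subject in clinic". The same footnote has the nurse explain how to complete the forms, and a nurse or physician is on hand for questions at the later visits.

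Section 7.2.1 places the "MFSI-SF and PROMIS questionnaires" at Cycle 1 Day 1. None is scheduled at screening, so this set is the analysis baseline. Section 11 (Analyses) states: "Subjects will have fatigue assessed at baseline and at weeks 2, 4, and 8". Its method is: "Repeated measures analysis of covariance will be used to assess the effect of Ginseng on fatigue". The test is placed as follows: "The primary hypothesis will be assessed using a linear contrast at the end of cycle 1".

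The sample size is worded in terms of change. Power is given for a mean change of 10 without ginseng and at least 27 with it, 17 units apart, with SDs of 27.0 (ginseng) and 26.1 (no ginseng). Section 11 also says the trial is not expected to reach significance, but that "we will be able to refine our estimate of the standard deviation for the fatigue score in this subject population".

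Section 11 does not mention mode of administration. Footnote 6 refers to the Study Procedures Manual for more detail; that manual is not among the documents.

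**The concern.** A change score compares two measurements and assumes both were made in the same way. Here one end is spoken to a member of the study staff and the other is filled in by the subject. If some subjects report fatigue differently in the two settings, that difference enters their change score. Because every baseline is an interview and no planned follow-up is, the data hold no contrast from which a mode effect could be estimated or removed.

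Two things are at stake. The first is the meaning of each arm's mean change, which would combine any mode shift with the effects of time, disease and treatment. The second is precision: mode response that varies between subjects loosens the link between baseline and follow-up. That widens the spread of change scores and reduces what baseline adjustment can gain. It matters somewhat more here because the trial's stated value lies largely in estimates for planning a further study.

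**Working it through.** **1. The plan's own figures.** Inputs from Section 11: difference 17, SDs 27.0 and 26.1, n = 60 and 30, two-sided 5%.

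- SE = √(27.0²/60 + 26.1²/30) = 5.904, with Satterthwaite df 59.9. Power by the noncentral t is 80.9%, against 80% stated.
- 95% half-width = 1.96 × 27 × √(1/60 + 1/30) = 11.833, as stated.

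Both are reproduced.

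**2. A shift of m points common to both arms** (m is assumed; the documents give none).

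| m | change, no ginseng | change, ginseng | difference |
|---|---|---|---|
| 0 | 10 | 27 | 17 |
| 5 | 15 | 32 | 17 |
| 10 | 20 | 37 | 17 |

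The within-arm changes move one for one with m. The difference, and therefore power, does not move.

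**3. Mode response that varies between subjects.** Assume independent mode noise with SD s, equal in both arms, added to the planned SDs: SD′ = √(SD² + s²).

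| s | SD′ ginseng | SD′ no ginseng | power at 17 | half-width (1.96 × SD′ ginseng × √0.05) |
|---|---|---|---|---|
| 0 | 27.00 | 26.10 | 80.9% | 11.83 |
| 5 | 27.46 | 26.57 | 79.5% | 12.03 |
| 10 | 28.79 | 27.95 | 75.5% | 12.62 |

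The ginseng-arm SD of change rises by 1.7% at s = 5 and by 6.6% at s = 10.

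**4. The same noise under covariate adjustment.** Here it degrades only the covariate. Assume that 27 is an SD of change, that baseline and follow-up variances are equal, and that their correlation is r. The cross-sectional variance is then V = 27²/[2(1 − r)]. Noise in the baseline turns r² into r²V/(V + s²), and the adjusted variance is proportional to one minus that quantity.

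With r = 0.60, V = 729/0.8 = 911.25:

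- s = 5: 0.36 × 911.25/936.25 = 0.350. The ratio 0.650/0.640 = 1.015, so the adjusted SD rises by 0.7%.
- s = 10: 0.36 × 911.25/1011.25 = 0.324. The ratio 0.676/0.640 = 1.056, so the adjusted SD rises by 2.7%.

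The same formula at r = 0.50 (V = 729) gives 0.6% and 2.0%. At r = 0.70 (V = 1215) it gives 1.0% and 3.6%. The loss is below the 1.7% and 6.6% of step 3 in each case.

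**5. How much noise would a large loss need?** Under the assumptions of step 4 with r = 0.60, lowering r to 0.55 needs the baseline variance multiplied by (0.60/0.55)² = 1.19, so s = √(0.19 × 911.25), about 13 points. Lowering r to 0.50 needs a factor of 1.44, so s = √(0.44 × 911.25), about 20 points. Nothing in the documents supports mode effects of that size.

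**The case against.** The strongest reply is that the plan does not test raw change. The primary analysis is a repeated measures ANCOVA with an arm contrast, and all post-baseline scores share one mode. A common shift goes into the intercept if baseline is a covariate, or into the visit term if baseline is a repeated response. The outcome rules in Section 11 (12 or larger, 8–12, close to zero) are also differences between arms. This stands, and it limits the point to within-arm change and precision.

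A reader might infer that the treatment estimate is biased. The documents do not support that: footnote 6 applies the same switch to both arms, and bias would need a mode effect that differs by arm. Treatment is open, so knowledge of the arm at a baseline taken after randomization could affect answers. But the documents do not fix the order of baseline and randomization, and that question concerns timing rather than mode.

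A reader might also infer that the SD the trial sets out to refine is necessarily corrupted. Section 11 speaks of the SD of the fatigue score. If that means the spread of follow-up scores, baseline mode does not touch it; if it means the SD of change, it does.

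The two settings should not be drawn too far apart either. Later forms are completed in clinic with staff available, not in private, and the procedures manual may standardize the interview. An opening interview can also help first-time responders and secure a complete baseline. That is a fair aim, but nurse instruction and help with questions already serve most of it without a second mode.

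**Conclusion.** The point holds in a limited form. Footnote 6 fully confounds mode of administration with baseline versus on-treatment, and nothing else in the documents removes this or allows for it. Each arm's mean change from baseline therefore includes any mode shift. Mode response that varies between subjects adds noise to change scores, to their SD if that is the SD used to size a follow-up trial, and to baseline as a covariate. The planned between-arm contrast and decision rules are unaffected by a shift equal in both arms.

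The size cannot be known from the documents. The power figures of 79.5% and 75.5% rest on assumed independent noise with an SD of 5 or 10 points and on a change-score calculation; the planned covariate model would lose less. This is a worthwhile, inexpensive improvement and not a threat to the primary comparison.

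**What to change.** Amend footnote 6 and the Study Procedures Manual so that the first MFSI-SF and PROMIS set is self-administered in clinic like the later ones. The nurse gives instructions, answers questions and checks completeness before the subject leaves. Allow interview only for a subject who cannot self-complete, keep that mode at every visit for that subject, and record the mode on the case report form.

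The cost is one sentence in the protocol, a matching change in the manual and one mode field, with slightly less nurse time. The downside is that a few first-time responders may skip items, which the completeness check handles. If the interview is kept, Section 11 should say that within-arm change from baseline includes any mode effect and should not be interpreted on its own.
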